## 8.2 ADVERSE EVENTS REPORTING TIMELINES

Life-threatening or fatal unexpected adverse events associated with the use of the study drug or procedures must be reported to the DSMB Chair and to the IRB within 24 hours of discovery of the incident with subsequent follow-up submission of a detailed written report.

The FDA will be notified by telephone or facsimile transmission of a human adverse event that is fatal or life-threatening no later than 7 calendar days after receiving the respective human adverse event information, followed by the subsequent submission of a written IND Safety Report.

Serious and unexpected adverse events associated with the use of the study drug or procedures will be reported within 48 hours to the DSMB Chair and the IRB with subsequent follow-up submission of a detailed written report in accordance with the respective policies and procedures of the IRB. Written IND Safety Reports will be submitted to the FDA as soon as possible and, in no event, later than 15 calendar days following the investigator-sponsor's receipt of the respective adverse event information. All AE and SAE will be reported to the DSMB quarterly.

A summary report of the findings will be prepared and submitted to the regulatory agencies as required.

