## 8. ADVERSE EVENTS

The proposed study will use the FDA definition of adverse events (AE) and serious adverse events (SAE). Any SAE, which is unexpected and related to study intervention, will be reported immediately to the IRB and FDA and will include all known details regarding the nature of the SAE. In the event that a participant either withdraws from the study or the investigators decide to discontinue a participant due to a SAE, the participant will be monitored by the PI and treating investigator until (a) a resolution is reached (e.g., the problem has resolved or stabilized with no further change expected), (b) the SAE is determined to be clearly unrelated to the study intervention, or (c) the SAE results in death. Outcomes of SAEs not previously reported will be reported to the sponsor, IRB and FDA via a follow-up report. A summary of the SAEs that occurred during the previous year will be included in the FDA annual progress report as well as in the annual IRB renewal.

The severity of adverse changes in physical signs or symptoms will be classified as follows:

- Grade 1 (Mild): asymptomatic or mild symptoms; clinical or diagnostic observation only; intervention not indicated.
- Grade 2 (Moderate): minimal, local or noninvasive intervention indicated; limiting age-appropriate ADL (Activities of Daily Living).
- Grade 3 (Severe): medically significant but not immediately life-threatening; hospitalization or prolongation of hospitalization indicated; disabling; limiting self-care/ADL.
- Grade 4 (Life-threatening): consequences; urgent intervention indicated.

- Grade 5 (Death): event is a direct cause of death.

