## 8.1 REPORTABLE ADVERSE EVENTS

For this study, a serious adverse event is any untoward clinical event that is thought by either the Principal Investigator, [name] or the sponsor, [name] to be unexpected and at least possibly related to the study and results in any of the following:

1. Death
2. A life-threatening adverse event
3. Inpatient hospitalization or prolongation of an existing hospitalization
4. A persistent or significant incapacity or substantial disruption of the ability to conduct normal life functions
5. A congenital anomaly or birth defect
6. Important medical events that may not result in death, be life threatening, or require hospitalization.
7. Hospitalization may be considered serious when, based upon appropriate medical judgment, they may jeopardize the patient, or subject, and may require medical, or surgical intervention to prevent one of the serious outcomes listed above.

If clinically important and unexpected adverse experiences or clinically important study-related adverse experiences occur, they will be recorded on the adverse event case report form.

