#### **10. WITHDRAWAL OF PARTICIPANTS AND STOPPING CRITERIA**

Life-threatening or fatal unexpected adverse events associated with the use of the study drug or procedures must be reported to the HRPO within 24 hours of discovery of the incident with subsequent follow-up submission of a detailed written report. The FDA must be notified by telephone or facsimile transmission of a human adverse event that is fatal or life-threatening no later than 7 calendar days after receiving the respective human adverse event information, followed by the subsequent submission of a written IND Safety Report.

Serious and unexpected adverse events associated with the use of the study drug or procedures must be reported to the HRPO with subsequent follow-up submission of a detailed written report in accordance with the respective policies and procedures of the HRPO. Written IND Safety Reports will be submitted to the FDA as soon as possible and, in no event, later than 15 calendar days following the investigator-sponsor's receipt of the respective adverse event information.

All reports noted in this section will also be provided to the NIA Program Officer and the DSMB.

**Consent:** During the consent process and when deemed appropriate by study staff throughout study, participants will also be informed that they are free to withdraw from the study at any time without any consequences.

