### **Discontinuation of the Clinical Trial**

#### **Stopping Rule:**

Extensive published literature and considerable local experience at University of Pittsburgh indicates nitrite is not inherently dangerous at the doses targeted in this trial. Certain side effects of nitrite are idiosyncratic in older frail patients and it is anticipated that there will be participants who do not tolerate the treatment who may need to be withdrawn from the study. Nonetheless, if a subject enrolled in the study experiences a fatal event that is directly attributable to the NO2, the overall study treatment will be discontinued.

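### Section 8.1 builds unexpectedness and relatedness into the SAE definition, so a drug-related hospitalization for a listed harm, if judged expected, need reach the DSMB only quarterly

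*Combined protocol and SAP*

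**What the plan says.** Section 8 opens with "The proposed study will use the FDA definition of adverse events (AE) and serious adverse events (SAE"), and sets the rule "Any SAE, which is unexpected and related to study intervention, will be reported immediately to the IRB and FDA". Read together, these make unexpectedness and relatedness conditions on how fast an SAE is reported, not on whether it is one.

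Section 8.1 gives a different definition. An SAE is an event that the principal investigator or the sponsor thinks "to be unexpected and at least possibly related to the study and results in any of the following", after which the usual serious outcomes are listed, hospitalization among them.

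Section 8.2 has two fast routes to the DSMB Chair. Fatal or life-threatening unexpected events go within 24 hours. For the rest, "Serious and unexpected adverse events associated with the use of the study drug or procedures will be reported within 48 hours". The default is "All AE and SAE will be reported to the DSMB quarterly".

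Section 6.1.1 lists hypotension and methemoglobinemia among the effects the investigators anticipate. The stopping-rule text in Section 10 adds that "it is anticipated that there will be participants who do not tolerate the treatment who may need to be withdrawn from the study". The plan does not define *unexpected*.

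**The concern.** The two definitions of an SAE cannot both apply. Under Section 8, a hospitalization for drug-induced hypotension is an SAE whatever anyone foresaw. Under Section 8.1, it is not an SAE if it was foreseen.

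The filter falls on the harms that the drug is known to be capable of causing, because those are the ones easiest to call expected. All participants are 70 or older, and Section 10 says that no dose below 20 mg three times daily is available. The board's report carries the recommendation to continue, change or terminate the study (Section 9.1). As written, whether the board must hear of such a hospitalization in two days or in a quarter depends on one undefined word.

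**Working it through.** The plan gives no figure of its own for this delay, so the check sets the reporting routes side by side, follows one case through them, and then does the interval arithmetic.

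**Routes to the DSMB**

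| Route | Section | Condition | Time limit to the DSMB |
|---|---|---|---|
| Expedited | 8.2 | fatal or life-threatening, unexpected, associated with drug or procedures | 24 hours |
| Expedited | 8.2 | serious, unexpected, associated with drug or procedures | 48 hours |
| Copies of Section 10 reports | 10 | fatal or life-threatening events; serious and unexpected events | none stated |
| Periodic | 8.2 | all AEs and SAEs | quarterly |
| Meetings | 9.1 | none stated | at least every six months; the Chair may call an emergency meeting |

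**Test case.** A participant is hospitalized for hypotension. It is not life-threatening, is judged related to the drug, and is judged expected because Section 6.1.1 lists it.

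1. Section 8.1: not an SAE, because it is not unexpected. Section 8: an SAE. The conflict is direct.
2. Section 8.2, 24 hours: does not apply (neither life-threatening nor unexpected).
3. Section 8.2, 48 hours: does not apply (not unexpected). This is so under either definition, because the route states that condition separately.
4. Section 10: "All reports noted in this section will also be provided to the NIA Program Officer and the DSMB". Those reports cover fatal or life-threatening events and serious, unexpected events, so the case is not among them. The FDA telephone or fax notice in Section 10 covers fatal or life-threatening events without requiring unexpectedness. Read literally, a life-threatening but expected event is therefore copied to the DSMB, though with no deadline. That is why the point is confined to events that are not life-threatening.
5. Section 9.2 sends all events at once to an investigator, then to the IRB under institutional requirements and to the IND sponsor. Sections 2.2.1 (Visit 4) and 10 send clinic and outpatient events to the principal investigator or a study physician. None of these names the DSMB.
6. Section 7.2 promises ongoing DSMB monitoring but gives no timetable or event criterion.
7. What remains is the quarterly report.

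**Delay**

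- Longest required wait: 365 / 4 = 91.25 days, about 91.
- Average wait, assuming that the event falls at a random time in the quarter and the report arrives at its end: 91.25 / 2 = 45.6 days, about 46.
- The same event judged unexpected: 48 hours = 2 days.
- Dosing period (synopsis: 14 weeks; Section 2.3.4: up to 16 weeks): 14 × 7 = 98 days to 16 × 7 = 112 days.

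**The two sections need repair together.** Correcting Section 8.1 alone leaves both fast routes closed to expected events. Adding a route for expected SAEs to Section 8.2 alone achieves nothing while Section 8.1 says that an SAE must be unexpected.

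**The case against.** The strongest reply is that a serious case would probably be called unexpected. Section 6.1.1 says that 60 to 120 mg of nitrite daily does not raise methemoglobin above 3% and has not been linked to clinically important hypotension. This trial gives 3 × 20 = 60 mg daily. The same section ties frequent hypotension to higher doses and calls methemoglobinemia rare. Against that text, an investigator could reasonably treat a hospitalization as unexpected and report it within 48 hours. This stands, and it makes the gap smaller. It does not close it: the judgement has no stated criterion, and Sections 6.1.1 and 10 also support the opposite answer.

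A second reply is that oversight is already substantial: immediate reporting to an investigator, IRB and sponsor reporting, participant-level rules for methemoglobin and hypotension, review of safety data as they arise (Section 9.4), and emergency meetings at the Chair's call. This also stands. The names in Section 9.4 are removed from the public copy, so the reviewer's role cannot be read. But that section states no duty to tell the board, and the Chair can call a meeting only about an event the Chair has heard of.

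Three stronger readings are tempting, and the documents do not support them.

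- A reader might infer that a participant could finish treatment before the board must be told, because a quarter exceeds 12 weeks. Dosing continues through the final visits, so planned exposure is 98 to 112 days, and both exceed 91.
- A reader might infer that the trial can be stopped only "if a subject enrolled in the study experiences a fatal event that is directly attributable to the" drug. That is the only automatic trigger, but Sections 9.1 and 9.3 provide for recommending or deciding on termination on benefit-risk grounds. The reporting gap does not show that another automatic trigger is needed.
- A reader might want a forecast of extra notices. The plan gives no rates for serious hypotension or methemoglobinemia. It lists vasovagal reaction to biopsy without a rate, and the second biopsy falls inside the post-dose monitoring window. Any total would rest on invented inputs.

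**Conclusion.** The point holds in a limited form. Sections 8 and 8.1 contradict each other on what an SAE is. Because both fast routes in Section 8.2 also require unexpectedness, a related, non-life-threatening hospitalization for a listed harm, if judged expected, has no required route to the DSMB faster than the quarterly report. The permitted delay is up to about 91 days, about 46 on average, against 2 days otherwise and 98 to 112 days of dosing.

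This rests on the event being judged expected, which the plan neither defines nor rules out, and on the average assuming uniform timing within the quarter. It is a gap in mandatory prompt notice to the DSMB, not in safety oversight as a whole, and it does not touch the efficacy analysis. It should be corrected because the correction is cheap and the present text leaves the outcome to an undefined word.

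**What to change.** 1. **Section 8.1:** delete the requirement that the event be unexpected and at least possibly related from the SAE definition, so that it agrees with Section 8. Removing only the word *unexpected* would leave relatedness in conflict. Keep both as separate conditions for expedited IRB and FDA reports.
2. **Section 8.2:** add: *Every SAE at least possibly related to study drug or procedures, and every methemoglobin value above 5%, will be reported to the DSMB Chair within 48 hours, whether or not expected (24 hours if fatal or life-threatening), with cumulative counts by arm from the unblinded statistician.*
3. If a hypotension trigger is wanted as well, limit it to events that lead to unblinding or withdrawal, so that vasovagal reactions around the biopsy do not generate notices.

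The 5% level (Section 10), the 24- and 48-hour windows (Section 8.2) and the unblinded statistician (Sections 2.3.5 and 2.3.10) are already in the plan. The fatal-event stopping rule stays as it is. The cost is a short text amendment, more events classed as SAEs in periodic summaries, and a few extra notices to the Chair, in a number that the plan does not allow to be estimated.

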## 9. DATA SAFETY MONITORING

### 9.1 DATA SAFETY MONITORING BOARD

The DSMB will also be expected to meet as needed, but not less than, every six months to provide an overall summary status report to the regulatory agencies. An emergency meeting of the DSMB may be called at any time by the Chair should participant safety questions or other unanticipated problems arise.

In addition, the DSMB Report addressing the following information will be submitted to the IRB at the time of continuing review annually or more often as required:

- A list of the research personnel who participated in the data and safety monitoring.
- The frequency of monitoring that took place during the renewal intervals and/or the dates that data and safety monitoring was conducted.
- A summary of cumulative data related to unanticipated problems (including adverse events) including a determination of causality and whether the risk to benefit assessment has changed.
- If appropriate, a summary of pertinent scientific literature reports, therapeutic developments, or results of related studies that may have an impact on the safety of study participants or the ethics of the research study.
- A summary of the outcome of reviews conducted to ensure subject privacy and research data confidentiality.

Final conclusions regarding changes to the anticipated benefit-to-risk assessment of the study participation and final recommendations related to continuing, changing, or terminating the study.

## **9.2 DATA SAFETY MONITORING PLAN**

Monitoring of safety and data quality in the proposed study will be the responsibility of all personnel on the project, with primary responsibility and supervision by the Investigator. The Institutional Review Board will approve the Statement of Informed Consent for the study and provide institutional oversight of data and safety issues. The study protocol will be approved prior to recruiting or obtaining consent from any participants. Moreover, the study will be reviewed at a minimum of annual basis (or more frequently as deemed necessary) by the IRB committee. Each participant will sign the Informed Consent Form described above prior to participating in the study. To ensure participant safety, once participants are enrolled in the study, study staff will immediately report all adverse and serious adverse events to one of the Investigators. The Investigator will, per institutional requirements, report them to the IRB for their review. These events should also be communicated to the sponsor of the IND. With regards to the monitoring of data quality and protected health information, all required personnel proposed for this project will have the required human participants and confidentiality training, which includes information about maintaining data integrity and security. Confidentiality will be guarded using established procedures such as storing data in locked cabinets within locked offices or locked data rooms, coding by study identification numbers rather than any personally identifying information to avoid revealing the identity of participants, and aggregating data across participants. The key linking names and study identification numbers will be kept separately from the data sets with limited access by study personnel. Only study personnel will have access to the data sets on protected servers. In order to maintain the highest standard of data entry quality, all data will be double entered, with discrepancies highlighted so that they can be reviewed by the project coordinator. Oversight of all aspects of data management will occur with the Investigator.

## **9.3 PARAMETERS TO BE MONITORED**

The following progress will be monitored throughout the course of the research to ensure the safety of participants as well as the integrity and confidentiality of their data.

- An evaluation of the progress of the research study, including subject recruitment and retention, and an assessment of the timeliness and quality of the data.

- A review of collected data (including adverse events, unanticipated problems requiring reporting and those captured on the non-compliance log, and subject withdrawals) to determine whether there is a change to the anticipated benefit-to-risk assessment of study participation and whether the study should continue as originally designed, should be changed, or should be terminated.
- An assessment of external factors or relevant information (e.g. pertinent scientific literature reports or therapeutic development, results of related studies) that may have an impact on the safety and study participants or the ethics of the research study.
- A review of study procedures designed to protect the privacy of the research participants and the confidentiality of their research data.

#### **9.4 FREQUENCY OF MONITORING**

[name] will review subject safety data as it is generated. [name] and the research staff will meet with bi-weekly and/or monthly (as they get further into the study) intervals to re-evaluate study goals, subject recruitment, data coding and retention, documentation and identification of adverse events, complaints and confidentiality of participants. There will be an evaluation of the progress of the research study, including assessments of data quality, timelines, participant recruitment, accrual, and retention. [name] will also review the outcome and adverse event data to determine whether there is any change to the anticipated benefit-to-risk ratio of study participation and whether the study should continue as originally designed or should it be re-evaluated and changed

#### **10. WITHDRAWAL OF PARTICIPANTS AND STOPPING CRITERIA**

Life-threatening or fatal unexpected adverse events associated with the use of the study drug or procedures must be reported to the HRPO within 24 hours of discovery of the incident with subsequent follow-up submission of a detailed written report. The FDA must be notified by telephone or facsimile transmission of a human adverse event that is fatal or life-threatening no later than 7 calendar days after receiving the respective human adverse event information, followed by the subsequent submission of a written IND Safety Report.

Serious and unexpected adverse events associated with the use of the study drug or procedures must be reported to the HRPO with subsequent follow-up submission of a detailed written report in accordance with the respective policies and procedures of the HRPO. Written IND Safety Reports will be submitted to the FDA as soon as possible and, in no event, later than 15 calendar days following the investigator-sponsor's receipt of the respective adverse event information.

All reports noted in this section will also be provided to the NIA Program Officer and the DSMB.

**Consent:** During the consent process and when deemed appropriate by study staff throughout study, participants will also be informed that they are free to withdraw from the study at any time without any consequences.

#### **Intervention Phase:**

Outpatient: If participants report change in skin tone and dizziness or other signs of methemoglobinemia for  $\geq 24$  hours, the need for an interim visit with the above described steps will be followed. The visit can be conducted in the UPMC Montefiore GRC or TRC, or in the Pepper Center-SMART Center.

At this visit, methemoglobin will be assessed. If greater than 5%, the PI will be unblinded to drug or placebo assignment. If participants are on nitrite, PI will evaluate data and make a determination regarding discharge on 20 mg tid. If discharged on 20 mg tid, participants will be contacted via phone for the next 2 days for symptom re-assessment. If symptoms remain resolved, participants will continue on 20 mg tid. If symptoms persist, participants will be requested to come in for repeat methemoglobin testing after 3 days. If level persists above 5%, participation in the study for the subject will be discontinued.

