### **Weekly Telephone Calls**

Following Visit 4, the study staff will contact participants by phone each week to review any symptoms. Staff will continue to call weekly until 1 week after visit 9. Each call will last approximately 5-10 minutes. We will ask participants if they have missed any study drug doses and if there have been any changes in their medications or medical history, including emergency room visits or hospitalizations since their study visit. We will ask participants to review their drug diary card to report what they wrote down for the week to help them remember.

We will also remind participants to contact the study staff or doctor anytime their health care team suggests a change in medications or if they have any symptoms that cause concern. There will be study personnel available to address participant's questions or concerns 24 hours/7 days a week.

During the drug intervention period, participants will also be asked about their activity levels, exertion levels, activity enjoyment, and barriers to activity as part of the weekly calls.

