## **6. POTENTIAL RISKS AND BENEFITS**

### **6.1 POTENTIAL RISKS**

### 6.1.1 Risk of Experimental Drug Intervention

Nitrite: Numerous studies have evaluated acute, subacute and chronic drinking water exposures of nitrate and nitrite in laboratory animals and drinking water and dietary exposures in humans. Recent studies are available using high doses of nitrite by oral route in the form of beet root juice. Recent studies have evaluated acute exposures of oral preparations of nitrite and nitrate on PK and BP and are characterized below. More extensive human data is available on parenteral sodium nitrite as it is currently available and approved by the FDA for use in the emergency treatment of cyanide poisoning. It is also notable that neutraceutical preparations are currently being sold with levels of nitrite (12.7 mg per tablet) and nitrate (3.9 mg per tablet).

Sodium nitrite has been used commercially as a food preservative, an anti-corrosive agent, a coloring agent, and an anti-anginal agent, with additional uses in laxatives, burn ointments, and liniments. Amyl nitrite has been inhaled or ingested as a euphoric stimulant. Nitrite has also been found as a contaminant in well water. Literature searches generated case reports of nausea, vomiting, abdominal pain, dizziness, headache, flushing, cyanosis, tachypnea, dyspnea, hypotension and death attributed to excess nitrite (high-dose) exposure from these sources as a consequence of methemoglobinemia due to oxidation of heme-iron in oxyhemoglobin. Normal background methemoglobin production is 1-3%. If levels of methemoglobin rise above approximately 30% of total hemoglobin, a subject may appear cyanotic and experience dyspnea, due to the reduced oxygen carrying capacity of hemoglobin (methemoglobin cannot bind oxygen). Levels above 50% can cause seizures, hypotension, coma and death. Sodium nitrite administration for cyanide poisoning at the labeled dosage of 300 mg causes methemoglobinemia, a desirable effect, as methemoglobin binds to cyanide, thus protecting cellular mitochondria. A standard dose of nitrite used for cyanide poisoning is 300 mg up to 600 mg. Note that methemoglobin levels have never risen higher than 3% at the currently used therapeutic doses (<75 mg) in 80 volunteers in phase I studies at the NIH.

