#### **As outpatient:**

If participants experience lightheadedness or dizziness after visit 4 while they are on the study drug/placebo, we request that they call the study coordinator who will inventory their symptoms, compare to baseline levels (measured at pK), and discuss need for an interim visit with study physician. If a visit is indicated, participants will be asked to repeat drug dosing of 20 mg with follow up methemoglobin and BP pressure monitoring. A study physician will factor relevant subject symptoms and hemodynamics and will confirm a management plan including the:

- need for un-blinding,
- need to discontinue and drop from the trial.

If participants proceed, they will be reassessed via phone each day for the next 2 days thereafter to ensure that the patient is stable. However, if there are continued symptoms, the physician investigator will reevaluate the patient's suitability for continued participation based on symptoms and/or hemodynamics.

If participants who were initiated report symptoms as described above, they will be asked to complete an interim visit, methemoglobin and BP pressure assessment; the physician may have to withdraw the subject since a dose lower than 20 mg tid is not an option.

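### After a methemoglobin level above 5%, the repeat test that decides discontinuation is triggered only by persisting symptoms, so a participant whose symptoms clear stays on full dose with no triggered repeat

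*Combined protocol and SAP*

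**What the plan says.** Section 10, Intervention Phase, covers a participant who reports signs of methemoglobinemia lasting 24 hours or more. An interim visit may follow, at which methemoglobin is measured. Above 5%, the PI is unblinded. For a participant on nitrite, the "PI will evaluate data and make a determination regarding discharge on 20 mg tid". Those sent home on drug are telephoned over the next 2 days about symptoms. The path then splits:

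- Symptoms gone: "If symptoms remain resolved, participants will continue on 20 mg tid".
- Symptoms still present: "If symptoms persist, participants will be requested to come in for repeat methemoglobin testing after 3 days".

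The discontinuation rule comes next: "If level persists above 5%, participation in the study for the subject will be discontinued".

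On what symptoms reveal, Section 6.1.1 says: "If levels of methemoglobin rise above approximately 30% of total hemoglobin, a subject may appear cyanotic and experience dyspnea". It gives normal background as 1-3%.

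Other checks exist. The Study Timetable (2.2.2) lists methemoglobin with vital signs at Visits 4 to 9. Weekly calls cover symptoms: "Following Visit 4, the study staff will contact participants by phone each week to review any symptoms". The hypotension steps in Section 10 begin "If participants experience lightheadedness or dizziness after visit 4 while they are on the study drug/placebo" and include a methemoglobin measurement when an interim visit is judged necessary.

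**The concern.** The stopping criterion is a laboratory level, but access to the laboratory test depends on symptoms. In the branch where symptoms clear, no written step produces the number that would show whether the criterion is met.

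That would be harmless if loss of symptoms were good evidence of a level below 5%. The protocol gives no basis for thinking so. It puts the visible signs at a far higher level, and Section 10 also manages dizziness, the other sign named in the Intervention Phase text, as a hypotension symptom. Dizziness could clear because blood pressure recovered while methemoglobin stayed where it was.

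At stake is the safety of a participant known to be on nitrite with a measured level above 5%. Section 10 also says that a dose below 20 mg tid is not available, so the choice is full dose or withdrawal, and the measurement that separates the two is not requested.

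**Working it through.** The plan gives no figure to reproduce. The check sets the two branches side by side and then times the gap.

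**Branches after discharge on 20 mg tid with a level above 5%**

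| | Symptoms persist | Symptoms resolved |
|---|---|---|
| Triggered repeat level | After 3 days | None |
| Dose meanwhile | 20 mg tid | 20 mg tid |
| Can the 5% rule be applied? | Yes, on the repeat | Not until a level is taken for another reason |

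**Symptoms against action level.** 30% / 5% = 6. Cyanosis and dyspnea are described at about six times the level that triggers the rule.

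**Wait for the next scheduled level.** Inputs are the timetable intervals in 2.2.2 and three doses a day.

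- Visits 4 to 5 and 5 to 6 are each 6 weeks ±5 days apart, so the longest interval is 42 + 5 = 47 days. Signs must last at least 24 hours before the interim visit, so the longest remaining wait is 47 − 1 = 46 days, or 46 × 3 = 138 doses.
- Between Visits 6 and 9 each gap is at most about 14 days, or 14 × 3 = 42 doses.
- In the symptomatic branch the wait is 3 days, or 3 × 3 = 9 doses.

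The 46 days is a worst case. It needs signs that begin straight after Visit 4 or 5, the widest visit window, and no later symptoms.

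**Do the other checks fill the gap?** Weekly calls ask about symptoms and yield no level. Section 9.4 has safety data reviewed as they arise, but in this branch none arises. The hypotension steps can yield a level, but only if dizziness or lightheadedness is reported. The scheduled readings do yield one. However, Section 10 does not tie its 5% rule to them, and the Visit 4 text speaks of a high level without a number.

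**How many participants.** Section 6.1.1 states "Note that methemoglobin levels have never risen higher than 3% at the currently used therapeutic doses" and describes 69 volunteers and 11 patients with sickle cell disease, 69 + 11 = 80 people. For 0 of 80, the exact one-sided 95% upper limit is 1 − 0.05^(1/80) = 0.0368. Applied to 35 nitrite participants this is 0.0368 × 35 = 1.29 expected above 3%. The rate above 5% cannot be larger. The 1.29 is an upper limit on an expected count, not a maximum. At a rate of 0.0368 the chance of two or more among 35 is 1 − 0.9632^35 − 35 × 0.0368 × 0.9632^34 = 1 − 0.269 − 0.360 = 0.37.

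**The case against.** The pathway is supervised. The symptoms-resolved branch is reached only after a physician who knows both the level and the arm has judged continuation acceptable, and that physician may order a repeat at any time. This stands: continuation is not automatic. But the written steps after that decision are telephone calls and continued dosing, and they ask for no level.

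A reader might infer that the participant is never measured again. The documents do not support that. Methemoglobin is scheduled at every visit from 5 to 9, and recurrent dizziness or lightheadedness can lead to a test under the hypotension steps, which have no 24-hour requirement. The gap is therefore confined to someone who stays symptom-free, and it lasts until the next scheduled visit.

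The discontinuation sentence directly follows the symptomatic branch, so it can be read as applying only to persistent elevation with symptoms. That is a coherent reading, and on it the proposed change widens who is discontinued. Even so, the plan gives no reason for treating the same persistent level differently according to symptoms.

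The 30% figure also cuts the other way: the documents describe no harm to a symptom-free person just above 5%. Section 2.3.3 reports that plasma nitrite returned to baseline about 3-6 hours after a dose, with only minor methemoglobin rises. This keeps the point small. That observation, however, comes from one healthy subject in another study on 20 mg of nitrite once daily (with nitrate), whereas here dosing continues three times a day in someone already found above 5%.

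Finally, the Intervention Phase text refers to interim-visit steps described above it, and no such steps appear earlier in Section 10 of the text available. The full interim procedure cannot be confirmed.

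**Conclusion.** The point holds as a minor participant-safety matter. For a nitrite participant above 5% whom the PI keeps on 20 mg tid and whose symptoms clear, the plan triggers no repeat level. The wait for the next scheduled reading is at worst about 46 days between Visits 4-5 or 5-6, and about 14 days or less between Visits 6-9, against 3 days when symptoms persist. On the protocol's own account, symptom resolution does not show that the level has fallen.

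The number affected should be very small. The case needs a level above 5%, signs for at least 24 hours, a decision to continue, resolution of symptoms and continued elevation. It is tempting to read the 0-of-80 record as proof that at most one of 35 participants could be involved. That does not follow: it treats an upper limit on an expected count as a maximum, and it assumes that those 80 people represent adults aged 70 or over treated for up to 16 weeks, which the documents do not show. Nor does the point imply bias or lost power: no estimate, power or error rate is affected.

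**What to change.** In Section 10, Intervention Phase, replace the sentence that makes the repeat test conditional on symptoms with: *All participants discharged on 20 mg tid after a level above 5% will return for a repeat methemoglobin test after 3 days, whether or not symptoms have resolved.* Leave the discontinuation sentence as it stands.

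This keeps the trial's own threshold, interval and test, and cuts the longest wait from about 46 days to 3.

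The cost is one short extra interim visit per affected participant, probably none or one in the whole trial. The downside is that a symptom-free participant who remains above 5% would be discontinued and might lose the post-treatment biopsy, and with it the primary outcome measurement.
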